## **2.3 Patient disposition, demographics and other baseline characteristics**

### **2.3.1 Safety evaluation part (Part 1, Japan only)**

Patient disposition, demographics and other baseline characteristics will be listed for all patients enrolled in the safety evaluation part.

### **2.3.2 Randomized part (Part 2)**

The FAS will be used for all baseline and demographic summaries and listings unless otherwise specified. Summaries will be reported by treatment arm and for all patients, and listings will be reported by treatment arm to assess baseline comparability. No inferential statistics will be provided.

#### **2.3.2.1 Basic demographic and background data**

All demographic and baseline disease characteristics data will be summarized and listed by treatment arm. Categorical data (e.g. gender, age groups: <60, 60-<65 and  $\geq$  65 years, race, ethnicity, WHO performance status) will be summarized by frequency counts and percentages; the number and percentage of patients with missing data will be provided. Continuous data (e.g. age, weight, height, body surface area (BSA)) will be summarized by descriptive statistics (N, mean, median, standard deviation, minimum and maximum). BSA will be calculated using Gehan and George formula:

$BSA[m^2] = 234.94 * (height[cm]^{0.422}) * (weight[kg]^{0.515}) / 10000$  using height and weight at baseline.

WBC at baseline will be categorized (<20, 20-<50, and  $\geq$  50  $10^9/L$ ) and summarized by frequency counts and percentages.

#### **Baseline stratification factors**

The number (%) of patients in each stratum (constructed by 3 FLT3 mutation status and 2 regimens) based on data obtained from the IRT system will be summarized overall and by treatment arm for the FAS. Discordances between the stratum recorded in IRT at the time of randomization and the actual stratum recorded in the clinical database through the data collected on eCRF will be cross-tabulated and listed.

#### **Diagnosis and extent of cancer**

Summary statistics will be tabulated for diagnosis and extent of cancer. This analysis will include the following: WHO 2016 classification of AML, and sub-classification of AML.

## **Medical history**

Medical history and ongoing conditions, including cancer-related conditions and symptoms entered on eCRF will be summarized and listed by treatment arm. Separate summaries will be presented for ongoing and historical medical conditions. The summaries will be presented by primary system organ class (SOC), preferred term (PT) and treatment arm. Medical history and current medical conditions will be coded using the Medical Dictionary for Regulatory Activities (MedDRA) terminology. The MedDRA version used for reporting will be specified in the CSR and as a footnote in the applicable tables/listings.

## **Cytogenetics**

Cytogenetic abnormality(ies) will be summarized.

## **Extramedullary involvement**

Location of extramedullary involvement at screening will be summarized.

## **Other**

All data collected at baseline will be listed.

### **2.3.2.2 Patient disposition**

Enrollment by country and center will be summarized for all screened patients and also by treatment group using the FAS. The number (%) of screened and the reason for screening failure will be displayed. Also, the number (%) of non-randomized patients and its reason will be displayed.

The following summaries will be provided overall and by treatment group using the FAS:

- Number (%) of patients who were randomized (based on data from IRT system)
- Number (%) of patients who were randomized but not treated study drug
- Primary reason for not being treated study drug
- Number (%) of patients who were treated study drug
- Number (%) of patients who are still on-treatment by therapy (induction, consolidation, continuation)
- Number (%) of patients who completed therapy (induction, consolidation, continuation)
- Number (%) of patients who discontinued the study treatment by therapy (induction, consolidation, continuation)
- Primary reason for study treatment discontinuation by therapy (induction, consolidation, continuation)
- Number (%) of patients who are ongoing the post-treatment follow-up
- Number (%) of patients who have discontinued from the post-treatment follow-up
- Reasons for discontinuation from the post-treatment follow-up
- Number (%) of patients who are alive on the survival follow-up
- Number (%) of patients who dead on the survival follow-up

- Number (%) of patients who have entered the survival follow-up but whose status is unknown

### **2.3.2.3 Protocol deviations**

The number (%) of patients in the FAS with any protocol deviation will be tabulated by deviation category (as specified in the study PD Specification) overall and by treatment group for the FAS. Major protocol deviations leading to exclusion from analysis sets will be tabulated separately overall and by treatment group. All protocol deviations will be listed.

Protocol deviations related to COVID-19 pandemic will be tabulated separately by deviation category, overall and by treatment. PD relationship to COVID-19 pandemic will be displayed in the listing for all protocol deviations.

### **2.3.2.4 Analysis sets**

The number (%) of patients in each analysis set (defined in [Section 2.2](#)) will be summarized by treatment group and stratum.

## **2.4 Treatments (study treatment, rescue medication, concomitant therapies, compliance)**

### **2.4.1 Safety evaluation part (Part 1, Japan only)**

Study treatment, prior concomitant and post therapies will be listed for all patients enrolled in the safety evaluation part.

### **2.4.2 Randomized part (Part 2)**

#### **2.4.2.1 Study treatment / compliance**

Duration of exposure, actual cumulative dose, dose intensity (DI) and relative dose intensity (RDI) will be summarized by cycle for induction and consolidation, treatment phase (induction, consolidation and continuation), overall (for the study drug only) and treatment arm, separately for each component of study treatment (Investigational drug, control drug and combination partner). The duration of exposure to study treatment will also be presented.

The number (%) of subjects who have dose reductions or interruptions, and the reasons, will be summarized by cycle for induction and consolidation, treatment phase (induction, consolidation and continuation), and overall, separately for each component of study treatment.

Subject level listings of all doses administered on treatment along with dose change reasons will be produced.

The safety set will be used for all summaries and listings of study treatment unless otherwise specified.

### **Duration of exposure to study treatment**

Duration of exposure to study treatment is considered by taking into account the duration of exposure to the investigational drug or control, and any combination partners:

Duration of exposure to study treatment (months) =  $\{(date\ of\ last\ administration\ of\ study\ treatment) - (date\ of\ first\ administration\ of\ study\ treatment) + 1\}/30.4375$ .

Summary of duration of exposure of study treatment will include categorical summaries (<1 month ;  $\geq 1$  month ;  $\geq 3$  months ;  $\geq 6$  months ;  $\geq 12$  months ;  $\geq 18$  months ,  $\geq 24$  months). based on clinically meaningful time intervals) and continuous summaries (i.e., mean, standard deviation etc.) using appropriate units of time.

### **Duration of exposure to investigational drug, control drug and combination partner**

The duration of exposure for the study drug (midostaurin/placebo), cytarabine, high dose cytarabine and daunorubicin (labeled as [medication] in the definitions below) will be calculated by cycle during induction and consolidation, by therapy (induction, consolidation and continuation, when applicable) and overall as below. Each durations will include the non-planned periods of temporary interruption of the medication for any reason:

- Duration of [medication] exposure (days) by cycle = number of days of administration during the cycle (including the days temporary interrupted).
- Duration of [medication] exposure (days) in induction/consolidation phase = sum of durations of [medication] exposure by cycle for all cycles during induction/consolidation phase.
- Duration of [medication] exposure (days) in continuation phase =  $[(date\ of\ last\ administration\ of\ [medication]\ during\ continuation\ phase) - (date\ of\ first\ administration\ of\ [medication]\ during\ continuation\ phase) + 1]$ .
- Overall duration of [medication] exposure (days) = sum of durations of [medication] exposure by cycle for all cycles in induction, consolidation, and continuation phases.

In a given cycle and for a given medication, the duration of exposure is equal to zero for patients who entered the cycle but did not take the medication during this cycle. It is missing for patients who did not enter the cycle.

The duration of exposure will be summarized descriptively by cycle, treatment phase (induction, consolidation and continuation), overall and treatment group. In addition, the duration of exposure will be summarized descriptively by cycle, treatment, overall, regimen and treatment group.

### **Cumulative dose**

Cumulative dose of a study treatment is defined as the total dose given during the study treatment exposure and will be summarized for each of the study treatment components.

The **planned cumulative dose** for a study treatment component refers to the total planned dose as per the protocol up to the last date of investigational drug administration.

The **actual cumulative dose** refers to the total actual dose administered, over the duration for which the subject is on the study treatment as documented in the DAR eCRF.

For patients who did not take any drug the cumulative dose is by definition equal to zero.

For continuous dosing, the actual cumulative dose is the sum of the non-zero doses recorded over the dosing period and the planned cumulative dose is the planned starting dose summed over the same dosing period.

For intermittent dosing, the actual cumulative dose should be defined based on the days when the subject is assumed to have taken a non-zero dose during dosing periods.

### **Dose intensity and relative dose intensity of study treatment**

The **Actual Dose Intensity (ADI)** for the study drug (midostaurin/placebo) is defined by cycle for induction and consolidation, by treatment phase (induction, consolidation and continuation) and overall as follows:

- ADI (mg / day) by cycle = (Cumulative dose during the cycle / duration of study drug exposure during the cycle).
- ADI (mg / day) by treatment phase = (Cumulative dose during the considered treatment phase / duration of study drug exposure during the considered treatment phase), for all patients who entered the considered treatment phase.
- Overall ADI (mg / day) = (Overall cumulative dose during the study / overall duration of exposure).

ADI for cytarabine, high dose cytarabine and daunorubicin (labeled as [medication] in the definitions below) is defined by cycle, and by treatment phase (induction and consolidation, when applicable) as follows (note: the Body Surface Area (BSA) reported at the beginning of each cycle should be taken into account in the calculations of the ADI for the considered cycle):

- ADI (mg/m^2/cycle) by cycle = ((Cumulative dose during the cycle / BSA at the beginning of the cycle)).
- ADI (mg/m^2/cycle) by treatment phase = (sum of (Cumulative dose during the cycle / BSA at the beginning of the cycle) for all cycles received during the considered treatment phase / number of cycle of which at least one [medication] is administered), for all patients who entered the considered treatment phase.

In a given cycle and for a given medication, the ADI is equal to zero for patients who entered the cycle but did not take the medication during this cycle. It is missing for patients who did not enter the cycle.

The **Planned dose intensity (PDI)** for the study drug (midostaurin/placebo) is defined, by cycle for induction and consolidation, by treatment phase (induction, consolidation and continuation), and overall as follows:

- PDI (mg/day) = 100 mg/day.

The PDI for cytarabine by cycle in the induction phase is defined as follows:

- PDI (mg/m^2 / cycle) during JALSG induction = 700 mg/m^2/cycle during each cycle.
- PDI (mg/m^2 / cycle) during RATIFY induction = 1400 mg/m^2/cycle during each cycle.

The PDI for high dose cytarabine by cycle in the consolidation phase is defined as follows:

- PDI (mg/m^2 / cycle) during JALSG consolidation = 20000 mg/m^2/cycle on each cycle.
- PDI (mg/m^2 / cycle) during RATIFY consolidation = 18000 mg/m^2/cycle on each cycle.

The PDI for daunorubicin by cycle in the induction phase is defined as follows:

- PDI (mg/m^2 / cycle) during JALSG induction = 250 mg/m^2/cycle on each cycle.
- PDI (mg/m^2 / cycle) during RATIFY induction = 180 mg/m^2/cycle on each cycle.

The PDI is not described but is used for the calculation of the Relative dose intensity (RDI).

The **Relative dose intensity** (RDI) is the percentage of planned dose that was actually received.

The RDI is defined for the study drug (midostaurin/placebo), cytarabine, high dose cytarabine and daunorubicin by cycle for induction and consolidation (when applicable), by treatment phase (induction, consolidation and continuation, when applicable) and overall as follows:

- RDI for the considered period (%) = ADI (mg or mg/m^2/day or cycle) for the considered period / PDI (mg or mg/m^2/day or cycle) for the considered period\*100.

In a given cycle and for a given medication, the RDI is equal to zero for patients who entered the cycle but did not take the medication during this cycle. It is missing for patients who did not enter the cycle.

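### In induction and consolidation, phase-level relative dose intensity leaves out any entered cycle in which the drug was wholly withheld, so it can overstate the dose received and can fall when more drug is taken

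*SAP*

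**What the plan says.** All of this is in SAP 2.4.2.1 unless stated otherwise.

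- **Meaning of RDI.** RDI is actual dose intensity (ADI) over planned dose intensity (PDI), times 100. In words, it "is the percentage of planned dose that was actually received".
- **By cycle.** For a given cycle and medication, "the RDI is equal to zero for patients who entered the cycle but did not take the medication during this cycle". A cycle never entered is missing.
- **Chemotherapy by phase.** The mg/m² summed over the cycles received is divided by the "number of cycle of which at least one [medication] is administered".
- **Study drug by phase.** ADI is "Cumulative dose during the considered treatment phase / duration of study drug exposure during the considered treatment phase". In induction and consolidation the duration is the "sum of durations of [medication] exposure by cycle for all cycles during induction/consolidation phase", and within a cycle "the duration of exposure is equal to zero for patients who entered the cycle but did not take the medication during this cycle".
- **Interruptions.** The same subsection on duration says that durations take in unplanned temporary interruptions.
- **Continuation.** "Duration of [medication] exposure (days) in continuation phase" is the last administration date minus the first, plus 1.
- **Overall.** Duration is the sum of by-cycle durations over all three phases. The overall summary is planned for study drug only.

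Protocol 10.3 defines dose intensity as cumulative dose over actual duration of exposure, and RDI as its ratio to planned dose intensity.

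**The concern.** A cycle entered without drug counts as 0% in the by-cycle table and does not count at all in the phase figure. Both are labelled RDI, and only the first agrees with the verbal definition. The zero-duration rule also conflicts with the statement that durations include unplanned interruptions, since a dose hold covering a whole cycle is such an interruption.

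The situation is foreseeable. The SAP writes explicit rules for cycles entered without the medication. Protocol Table 6-2 allows a study-drug hold for QTcF prolongation to run into the next cycle, and protocol 6.4.2 requires interruption while an unavoidable drug with known torsades risk is given. In consolidation, a patient can receive cytarabine in the first week and no study drug on Days 8 to 21.

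At stake is the reading of the phase-level RDI tables as a summary of how much drug was delivered in each arm. Complete loss of a cycle's dosing raises no flag there, while partial loss does.

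**Working it through.** **Step 1. Planned intensities.** Protocol Table 6-1 reproduces every PDI in the SAP:
- study drug: 50 × 2 = 100 mg/day
- cytarabine induction: 100 × 7 = 700 (JALSG) and 200 × 7 = 1400 mg/m² (RATIFY)
- high-dose cytarabine: 2000 × 2 × 5 = 20000 (JALSG) and 3000 × 2 × 3 = 18000 mg/m² (RATIFY)
- daunorubicin: 50 × 5 = 250 (JALSG) and 60 × 3 = 180 mg/m² (RATIFY)

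The PDIs are right; the problem lies in the ADI denominators.

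**Step 2. Study drug, four consolidation cycles entered.** A full cycle is 14 days (Days 8 to 21) × 100 mg = 1400 mg, so 5600 mg is planned. Held days inside a started cycle count as exposure, as the SAP's by-cycle duration states.

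| Illustrative patient | SAP: mg / days | SAP phase RDI | Received / planned |
|---|---|---|---|
| 3 full, 1 wholly withheld | 4200 / 42 | 100% | 4200 / 5600 = 75% |
| 3 full, 1 with Day 8 taken then held to Day 21 | 4300 / 56 | 76.8% | 4300 / 5600 = 76.8% |
| 3 full, 1 with 7 of 14 days taken | 4900 / 56 | 87.5% | 4900 / 5600 = 87.5% |
| 2 full, 1 wholly withheld, 1 with 3 days taken then held | 3100 / 42 | 73.8% | 3100 / 5600 = 55.4% |

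The SAP formula agrees with dose received whenever at least one dose is taken in every entered cycle. It fails only when a cycle has none. Comparing the first two rows, 100 mg more drug lowers RDI from 100% to 76.8%.

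**Step 3. Chemotherapy.** SAP phase RDI = (sum of mg/m² ÷ cycles with an administration) ÷ PDI. The alternative divides by cycles entered.

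| Illustrative patient | SAP | All entered cycles |
|---|---|---|
| RATIFY high-dose cytarabine: 18000 × 3, then 0 | 54000 / 3 / 18000 = 100% | 54000 / 4 / 18000 = 75% |
| RATIFY: 18000, 18000, 12000, 0 | 48000 / 3 / 18000 = 88.9% | 48000 / 4 / 18000 = 66.7% |
| Daunorubicin, RATIFY: 180, 0 | 180 / 1 / 180 = 100% | 180 / 2 / 180 = 50% |
| JALSG high-dose cytarabine: 20000, 0, 0 | 20000 / 1 / 20000 = 100% | 20000 / 3 / 20000 = 33.3% |

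Every row assumes that the undosed cycle was entered. The JALSG row needs two such cycles.

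**Step 4. Continuation, 12 cycles of 28 days.** With one cycle withheld between first and last dose, the span is 12 × 28 = 336 days and the dose 11 × 2800 = 30800 mg. That gives 91.7 mg/day, so RDI is 91.7%, which is correct.

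**Step 5. Overall, study drug.** Take 1 induction, 4 consolidation and 12 continuation cycles.
- One consolidation cycle withheld: dose 1400 + 4200 + 33600 = 39200 mg. SAP duration is 14 + 42 + 336 = 392 days, giving 100%. Counting the 14 withheld days: 39200 / 406 = 96.6%.
- One mid-continuation cycle withheld: dose 1400 + 5600 + 30800 = 37800 mg. With durations summed by cycle, 37800 / 378 gives 100%. With the continuation date span, 37800 / 406 gives 93.1%. The SAP's two duration rules thus give different overall figures.

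**Step 6. Edge case.** If the drug is withheld in every entered cycle of a phase, phase ADI in induction or consolidation is 0/0. The SAP has no phase-level rule for this.

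**The case against.** The best defence is that dividing by time on drug is a recognised choice. Protocol 10.3 defines dose intensity by actual duration of exposure, the SAP's study-drug formula follows it, and only the verbal description of RDI is loose. This explains the form of the formula but does not save it: the SAP's own durations include unplanned interruptions, so a wholly withheld cycle belongs in the duration.

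Several other objections stand and limit the point.

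- **Continuation.** A reader might infer that every phase is affected. Step 4 shows otherwise for cycles withheld between first and last dose.
- **Exactly 100%.** This arises only when every dosed cycle was at full dose. A hold that first truncates one cycle and then removes the next gives a figure such as 73.8%, which is still too high.
- **The 33% case.** It assumes that later JALSG consolidation cycles are entered without high-dose cytarabine. Protocol 6.1.1.1 describes each consolidation cycle as containing it, and Table 6-2 does not say that cycles continue without it. Cycles not entered are missing by design.
- **Repeated holds.** The protocol discontinues treatment after more than 28 consecutive days of study-drug interruption, which limits consecutive missed cycles.
- **Concealment.** A reader might infer that withheld cycles, or an excess of them on midostaurin, are hidden. By-cycle RDI of 0, cumulative dose by cycle and phase, interruption tables with reasons and dose listings all show them. The documents give no count of withheld cycles by arm, so no direction of bias between arms can be claimed.

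**Conclusion.** The point holds for phase-level RDI of cytarabine, high-dose cytarabine and daunorubicin, and of study drug in induction and consolidation. One wholly withheld cycle of four moves phase RDI from 75% to 100% when the other cycles are full. The measure is also non-monotone and, in one case, undefined. The overall study-drug figure, read literally, carries a small error: 3.4 percentage points for one withheld consolidation cycle in a full course.

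The sizes come from constructed patients and rest on two assumptions: the undosed cycle is recorded as entered, and held days within a started cycle count as exposure. How often this happens cannot be told from the documents.

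These are descriptive exposure summaries. EFS and the success criterion do not depend on them. The correction is worth making because the figure disagrees with its own definition and is cheap to put right.

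**What to change.** 1. **Chemotherapy phase ADI:** divide the summed mg/m² by the number of cycles entered in the phase.
2. **Study drug, induction and consolidation:** when a cycle is entered and no study drug is taken, count its 14 planned dosing days in the phase duration. This keeps the duration-based definition in protocol 10.3, matches the by-cycle RDI of 0, and turns the 0/0 case into 0%. Started cycles need no change.
3. **Overall study-drug RDI:** carry these durations forward, and use the existing first-to-last-dose span for the continuation component.
4. Leave cycles not entered as missing, reconcile the zero-duration sentence with the statement on interruptions, and record the change in SAP section 4.

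The cost is a few lines of SAP text, minor programming and a somewhat less favourable RDI. One limitation remains: a patient who enters a cycle but leaves before Day 8, for example through death or transplant, is charged 14 undosed days. By-cycle RDI already scores that patient 0, so the two tables would at least agree; a footnote can say so.

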### **Dose reductions, interruptions or permanent discontinuations**

The number of subjects who have dose reductions, permanent discontinuations or interruptions, and the reasons, will be summarized by cycle for induction and consolidation, treatment (induction, consolidation and continuation), and overall (only for the study drug), separately for each component of study treatment.

‘Dose change’, ‘Dose interrupted’, and ‘Dose permanently discontinued’ fields from the DAR eCRF will be used to determine the dose reductions, dose interruptions, and permanent discontinuations, respectively. The corresponding fields ‘Reason’ and ‘Reason for permanent discontinuation’ will be used to summarize the reasons.

A dose change is either ‘change in prescribed dose level’ or ‘dosing error’ where actual dose administered is different from the prescribed dose.

For the purpose of summarizing dose reduction, interruptions and their reasons, in case multiple entries for dose reduction/interruption that are entered on consecutive days with different reasons will be counted as separate reductions/interruptions. However, if the reason is the same in this mentioned multiple entries on consecutive days, then it will be counted as one reduction/interruption.

Dose reduction is defined as the dose change where the prescribed dose level is lower than the previous prescribed dose level or where the actual dose administered is lower than the calculated dose amount based on the prescribed dose. Therefore any dose change to correct a dosing error will not be considered a dose reduction. Because only dose change is collected in the CRF, dose reductions will be clarified programmatically using the definition above.

